1. STUDY OVERVIEW

Background and rationale

A frequent cause of acute low back pain with radiating leg pain is lumbar disc herniation (LDH) [1]. The diagnosis of lumbar disc herniation with radiculopathy is based on history and physical examination. Muscle testing, sensory testing, test of reflexes, straight leg raising test, Lasegue sign and crossed straight leg raising tests are commonly used. To confirm the diagnosis or in cases of clinical disagreement Magnetic Resonance Imaging (MRI) is recommended [1, 2]. However, intervertebral disc herniations and protrusions are also frequently found on MRI in asymptomatic patients [3, 4].

Quantitative Sensory Pain Testing (QST) is a well-defined psychophysical method that standardizes a potentially painful stimulus and quantifies the pain response from the test subject, making it possible to investigate pain processing [5, 6].

Only few studies have investigated the clinical value of (QST) responses in patients with low back pain [7] and it has not yet been shown if the pain sensitivity is different at the level of disc herniation.

Objectives

The aim of this study is to investigate whether the segmental level of disc herniation correlates with pain thresholds in patients with lumbar disc herniation. The hypothesis is that the lowest pain threshold is at the affected level.

The specific objective is to investigate whether patients are sensitized at the level of disc herniation when examined by quantitative sensory testing, in terms of pressure pain and heat pain sensitivity.

Methods

The data from the present study were part of a prospective, 4-year observational study of patients with sciatica due to lumbar disc herniation. This study will be based on data from the baseline examination.

PICOTS

Population:

Patients were consecutively recruited between November 2018 and January 2021 from three different hospitals in Denmark; a) The Spine Center of Southern Denmark at Lillebaelt University Hospital, b) The Department of Neurosurgery at Odense University Hospital and c) The Department of Rheumatology at Frederiksberg Hospital.

Participants were thus all patients recruited in a hospital setting on referral from primary sector.

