Inclusion criteria were 18+ years of age and legally competent, fluent in Danish (written and spoken), an MRI-verified disc herniation in the lumbar spine, complained of low back pain radiating below the knee or anterior thigh pain in one or both legs, pain distribution was of a dermatomal pattern, the reported average pain intensity was 3 or more on a Numerical Rating Scale (0-10 NRS), no history of previous spine surgery, surgery in general in the past 4 months, no current use of anticoagulants and/or confounding diagnoses e.g. lumbar spinal stenosis, local muscle trauma, cancer metastases, fibromyalgia and neuropathy.

Exposure:

Distance from segmental level of disc herniation: Clinical and MRI verified symptomatic level of disc herniation is labeled 0, the segmental level above and under is labeled +1 and so forth.

Outcomes:

QST measurements: Pressure Pain Threshold, kPa (PPT) and Heat Pain Threshold, °C (HPT).

Study design:

Observational cross-sectional study.

Further statistical details

Power considerations:

The current sample size had been estimated, based on previous experience and publications in the fields of QST. We had enlisted the assistance of a bio-statistician from the Institute of Regional Health Service Research. Since the project's main objective was to investigate predictor variables, there would be no hypothesis testing, and therefore no statistical basis for a power calculation. The sample size would suffice to demonstrate a statistically significant correlation at a level deemed too also be clinically relevant. The sample size was also in accordance with the previous literature in the field.

Framework:

This is an observational study assessing if patients are sensitized at the level of disc herniation when examined by QST. The data from the present study is part of a prospective, 4-year observational study of patients with sciatica due to lumbar disc herniation.

Timing of final analysis: The statistical analyses are expected to be initiated when this statistical analysis plan has been finalized and signed.

Timing of outcome assessment: (see next section)

Confidence intervals and P values: All 95% confidence intervals and P-values will be two-sided.

Multiplicity: No explicit adjustments but hierarchical testing of primary and secondary analyses as indicated by the order in the outline (Figure 2 is primary).

Statistical software: R version 4.2.2 (or newer).

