3. OUTCOMES AND DATA

Data management:

In general for both Pressure Pain Threshold and Thermal Pain Threshold:

Initially, 5 test-sites were marked with a black felt-tip pen in the lumbar region. Patients identified the most painful side (right/left) and the markings were made 2 cm lateral of the spinous process of L1-L5 identified by palpation.

For each stimuli (heat and pressure) we performed the QST tests twice at each test-site. The average of the two measurements at each test-site were used for further analysis. The test order of lumbar test sites was determined a-priori as a computer-generated randomized order for each participant.

Pressure Pain Threshold:

Pressure was applied manually with a Somedic algometer type II (Hörby, Sweden, 1 cm² probe) on the marked test-sites, with a near-constant increase in pressure of 50 kPa/s until the participant indicated the pressure becoming painful by pressing an indicator button connected to the algometer.

Thermal Pain Threshold:

With a Medoc TSA-II thermode stimulator the heat pain threshold was measured on the marked test sites. The thermode stimulator had a baseline temperature of 32°C and increased 1°C/s. The patient indicated when the stimulus was perceived as becoming painful by pressing an indicator button, upon which the temperature returned to baseline (decrease 10°C/s).

Patient-Reported Outcomes:

Age
Sex
Height
Weight
Back pain intensity
Leg pain intensity
Previous pain
Use of pain medication
Physical activity
Alcohol status
Work status
Sick leave

Roland-Morris Questionnaire: Assessment of physical disability due to low-back pain.

EQ-5D Questionnaire: Assessment of health-related quality of life.

PainDetect Questionnaire: Assessment of pain and neuropathic components.

Pain drawing: A pain drawing, was filled out by pen-on-paper. This was transformed to a digital PDF, where the total area of pain was calculated as number of pixels.

Segmental level of disc herniation (diagnose)

As recorded in the participants hospital journal and verified by MRI.

Data validation:

All variables used in the analyses, will be checked for missing values, outliers and inconsistencies.

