5. OUTLINE

The anticipated (predefined) outline of the manuscript is illustrated below.

Results that only will be presented in the manuscript text include:

- Number of participants included from Frederiksberg, Odense and Middelfart, respectively.
- Days on sick leave among those currently on sick leave.
- Duration of pain medication intake in days among those currently using pain medication.
- Further detailed results from the regression models visualized in figure 2 and 3.

Figure 1. Flow diagram

Anticipated plot design, illustrating potential reasons for exclusion:

[figure not shown]

Table 1. Patient characteristics

Characteristics	Total (n=)
Demographics	
Age, years	
Female, n(%)	
Body Mass Index, kg/m ²	
Back pain intensity, NRS (0-10)	
Leg pain intensity, NRS (0-10)	
Previous pain, n(%)	
Use of pain medication, n(%)	
Physical activity:	
Inactive, n(%)	
Low-impact physical activity ≥ 4 hours/week, n(%)	
High-impact physical activity ≥ 3 hours/week, n(%)	
Don't know, n(%)	
Smoking status:	
No, I don't smoke cigarettes, n(%)	
Yes, I smoke cigarettes only occasionally, n(%)	
Yes, I smoke 1 to 4 cigarettes per day, n(%)	
Yes, I smoke 5 to 14 cigarettes per day, n(%)	
Yes, I smoke 15 to 24 cigarettes per day, n(%)	
Yes, I smoke 25 or more cigarettes per day, n(%)	
Don't know, n(%)	
Alcohol status, units per week:	
0, n(%)	
1-7, n(%)	
8-14, n(%)	
15 or more, n(%)	
Don't know, n(%)	
Work status:	
Employed (eg. ordinary job, studying), n(%)	
Unemployed (eg. Senior or early retirement pension), n(%)	
Don't know, n(%)	
Sick leave, n(%)	
Questionnaires	
Roland-Morris Questionnaire	
EQ5D-3L, index score	
EQ5D-3L, VAS (0-100)	
PainDetect Questionnaire:	
Score ≥ 18, n(%)	
Score 13-18, n(%)	
Score <13, n(%)	
Pain drawing	
Pain drawing, pixels	
Segmental level of disc herniation (diagnose)	
L1, n(%)	
L2, n(%)	
L3, n(%)	
L4, n(%)	
L5, n(%)	

Further statistical information related to table 1:

Data will be presented as mean with standard deviation (SD) when normally distributed or as median with interquartile range in case of non-parametric data. Dichotomous and categorical data will be presented in proportions and/or frequency/count. Normality of the data will be assessed using Q-Q plots, and histograms.

[figure not shown]
Table 2. Quantitative Sensory Testing outcome measures

	Segment	n	Mean (SD)
Outcome			
Pressure Pain Threshold	All		
	L1		
	L2		
	L3		
	L4		
	L5		
Heat Pain Threshold	All		
	L1		
	L2		
	L3		
	L4		
	L5		

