Further statistical information related to table 2:

Data will be presented as mean with standard deviation (SD) when normally distributed or as median with interquartile range in case of non-parametric data. Normality of the data will be assessed using Q-Q plots, and histograms.

[figure not shown]
Figure 2: The association between the distance from the segmental level of disc herniation and pressure pain sensitivity (panel A) and heat pain sensitivity (panel B).

Values are least-squares means from a linear mixed models including the participant as random effect, distance from symptomatic disc herniation (5 levels; 0, 1, 2, 3, 4 segments) as fixed effect, as well as the value at 0 segments as covariate. Missing data for a specific distance will be handled implicitly by the repeated measures mixed linear models, assuming data missing at random (MAR). Error bars will indicate standard errors.

Assumptions will be checked by visual inspection of residual plots assessing the normality of residuals. In case the distributional assumptions do not hold, we will use an appropriate transformation (e.g., log-transformation in the case of right-skewed data and report the results as geometric means and geometric mean ratios), and/or, use non-parametric methods.

Figure 3: The association between the distance from the segmental level of disc herniation and pressure pain sensitivity (panel A) and heat pain sensitivity (panel B), stratified by site of symptomatic disc herniation.

Values are least-squares means from a linear mixed models including the participant as random effect, distance from symptomatic disc herniation (5 levels; 0, 1, 2, 3, 4 segments) and site of symptomatic disc herniation (5 levels, L1, L2, L3, L4, L5) as fixed effects, their interaction, as well as the value at 0 segments as covariate. Missing data for a specific distance will be handled implicitly by the repeated measures mixed linear models, assuming data missing at random (MAR).

Error bars will indicate standard errors.

SUPPLEMENTARY MATERIAL

The anticipated (predefined) supplementary material of the manuscript is illustrated below.

Supplementary file 1. This SAP

Supplementary Table 1. Patient characteristics by site of symptomatic disc herniation

Characteristics	L1 (n=)	L2 (n=)	L3 (n=)	L4 (n=)	L5 (n=)
Demographics					
Age, years					
Female, n(%)					
Body Mass Index, kg/m ²					
(...etc. as shown in Table 1)					

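### The Figure 2 and 3 models use the threshold at the herniation level as both an outcome and a covariate, so the planned SE bars have no clear meaning and the MAR statement fails at distance 0

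*SAP*

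**What the plan says.** Section 5 (Outline), under Figure 2, plots least-squares means from a linear mixed model with a random participant effect and distance from the herniation as "5 levels; 0, 1, 2, 3, 4 segments) as fixed effect, as well as the value at 0 segments as covariate". Under Figure 3 the model adds herniation site, and again includes "their interaction, as well as the value at 0 segments as covariate". On display it says: "Error bars will indicate standard errors". On missing values it says: "Missing data for a specific distance will be handled implicitly by the repeated measures mixed linear models, assuming data missing at random (MAR"), with no exception for distance 0.

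Section 1 gives the context. Under Multiplicity, the testing order is "as indicated by the order in the outline (Figure 2 is primary"). Under Objectives: "The hypothesis is that the lowest pain threshold is at the affected level". Section 3 states that "5 test-sites were marked with a black felt-tip pen in the lumbar region", so each participant has a distance-0 measurement by design. Beyond the bars, Section 5 promises for the text "Further detailed results from the regression models visualized in figure 2 and 3", without naming a contrast.

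**The concern.** Adjusting for a reference value is coherent when that value is not itself among the outcomes. Here it is. In the distance-0 rows the threshold is regressed on itself: the true slope is 1 and nothing is left to vary. In the other rows the true slope is the within-person correlation. The model forces one slope and one residual structure on both.

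Three things are at stake:

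- the precision shown in the primary figure, above all at distance 0, the level the hypothesis is about;
- the heights of the site curves in Figure 3, since every site is evaluated at one common distance-0 value;
- the missing-data claim. A missing distance-0 value is a missing covariate on all of that participant's rows, and ordinary mixed-model fitting drops them all.

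**Working it through.** The SAP states no sample size, SD, correlation, site mix or missing rate, so there is no figure of its own to reproduce. Everything below rests on labelled assumptions: total SD 1, within-person correlation ρ, n participants. The closed forms use one row per distance, as when every herniation is at L5.

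**1. Standard errors in Figure 2.**

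- Pooled slope: b = (1 + 4ρ)/5, so 1 − b = 4(1 − ρ)/5.
- Residual variance of the participant mean given the covariate: b(1 − b).
- Within-person part: 4(1 − ρ)/5.
- Their sum is n × (printed SE)² = (1 − ρ)(24 + 16ρ)/25, the same at every distance. At ρ = 0.8: 0.2 × 36.8/25 = 0.294, square root 0.54.
- Marginal SE: 1/√n.
- Correct conditional SE: 0 at distance 0 and √(1 − ρ²)/√n elsewhere.

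| ρ | slope b | printed SE × √n | marginal SE × √n | conditional SE × √n, distance 0 / 1–4 | printed v marginal |
|---|---|---|---|---|---|
| 0.5 | 0.60 | 0.80 | 1.00 | 0 / 0.87 | 20% shorter |
| 0.7 | 0.76 | 0.65 | 1.00 | 0 / 0.71 | 35% shorter |
| 0.8 | 0.84 | 0.54 | 1.00 | 0 / 0.60 | 46% shorter |
| 0.9 | 0.92 | 0.39 | 1.00 | 0 / 0.44 | 61% shorter |

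REML simulation (1000 replicates, n = 100) agrees. For ρ = 0.5/0.7/0.8 the printed SE is 0.0799/0.0651/0.0542, while the means actually vary with SD 0.097 to 0.105.

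With an unbalanced mix (assumed L1–L5 = 2/3/10/40/45%, ρ = 0.8), the printed SEs at distances 0–4 are 0.054/0.048/0.053/0.056/0.074 against empirical SDs of 0.098/0.097/0.099/0.102/0.111.

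A separate check in kPa (n = 100, between/within SD 120/60, so ρ = 0.8) gives 7.27 printed, 13.42 marginal and 8.05 conditional. Without the covariate the model prints 13.43, matching the marginal SE. With distance 0 removed from the outcome it prints 8.03, matching the conditional SE.

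**2. Contrasts against distance 0, complete data.** The SE is √(2(1 − ρ))/√n. In the balanced case contrasts and SEs are identical with and without the covariate (0.0998/0.0775/0.0632 for ρ = 0.5/0.7/0.8, n = 100). In the unbalanced mix the mean contrasts differ by at most 0.0003 SD, and the SEs by about 1% at most (0.0811 v 0.0820 at distance 4).

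**3. Figure 3.** A true level difference between sites is shown multiplied by 1 − b. For L4 v L5 with a true difference of 0.30 SD (n = 200), the difference shown at distance 0 is 0.12/0.07/0.05/0.02 SD for ρ = 0.5/0.7/0.8/0.9; at ρ = 0.8, 0.30 × 0.16 = 0.05. Within-site distance contrasts are identical with and without the covariate.

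**4. Missing distance 0.** Rates and mechanisms are assumed; true means and contrasts are 0.

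- 5% missing completely at random: no bias; contrast SE 0.0649 v 0.0642.
- Extreme MAR, where the participants with the lowest mean of the other four thresholds lose distance 0. Shifts under the planned model, in SD:

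| missing | ρ | least-squares means | contrasts |
|---|---|---|---|
| 5% | 0.8 | +0.10 | +0.005 to +0.008 |
| 5% | 0.5 | +0.07 to +0.09 | about +0.02 |
| 10% | 0.8 | +0.17 to +0.18 | about +0.013 |
| 10% | 0.5 | +0.13 to +0.16 | about +0.03 |

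The contrast shifts go towards the hypothesis. Without the covariate, the same data give errors of at most 0.007 (means) and 0.004 (contrasts), which is simulation noise.

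- Milder, probabilistic MAR (kPa, SD 120/60, total SD √(120² + 60²) = 134.2): with 5/10/20% missing, the distance-0 mean is 283.1/288.5/298.3 under the planned model and 279.4/280.7/280.6 without the covariate. The gaps of 3.7/7.8/17.7 kPa, divided by 134.2, are 0.03/0.06/0.13 SD.
- 20% missing at distance 2 instead: no bias under the planned model. The failure is specific to distance 0.

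**The case against.** The strongest reply is that the hypothesis is a within-person comparison, and step 2 shows that comparison is intact with complete data. This stands, and it limits the finding: the complete-data test of distance is not invalidated.

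Next, the marginal SE is not the natural yardstick for a within-person question. Against the conditional SE at distances 1–4 the bars are only 8 to 10% short (0.80/0.87 to 0.39/0.44, before rounding). Removing the covariate and changing nothing else would even make the bars a poorer guide to differences. At ρ = 0.8, two planned bars combined as if independent give 0.77/√n, two marginal bars give 1.41/√n, and the true SE of the difference is 0.63/√n. This also stands, and it is why the fix must include intervals for the differences. It does not rescue bars that estimate no defined quantity.

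Third, equalising sites in Figure 3 is what such a covariate does, and no objective compares absolute levels between sites. That is fair, but the caption announces no adjustment, and a reader will compare the curves' heights.

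Fourth, all five sites are tested in everyone, so distance 0 is missing only when a measurement fails, and row deletion is the default of ordinary software rather than something the SAP prescribes. True; but the SAP specifies no imputation or joint model that would avoid it.

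Finally, Section 1 mentions two-sided confidence intervals and P values, and the log-transformation fallback under Figure 2 mentions geometric mean ratios, so contrasts are foreseen in general terms. Neither passage says which contrast carries the primary result.

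**Conclusion.** The concern holds, and the plan should be changed before analysis. As written, the SE bars in the primary figure are neither marginal nor conditional SEs. This held at every correlation tried; how far off they are depends on the assumed correlation. Figure 3 compresses level differences between sites, to about one sixth at ρ = 0.8 (factor 0.16). The MAR statement is untrue for distance 0 under ordinary fitting and remains true for distances 1–4. The practical effect of that last part cannot be sized from the SAP: none in bias if failures are completely at random, and mainly on the plotted means rather than the contrasts otherwise. With distance-0 values present, the Figure 2 means, the contrasts against distance 0 and the within-site contrasts in Figure 3 are essentially unaffected.

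**What to change.** Delete the covariate clause from the model descriptions under Figures 2 and 3. Keep all five distances as outcomes with the random participant effect. Add one sentence naming the inferential result: the within-participant differences, distance k minus distance 0 for k = 1 to 4, from the same model, with two-sided 95% confidence intervals.

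An alternative is to keep the covariate and model distances 1–4 only. That gives correct conditional SEs, but it still loses every participant without a distance-0 value, so it would need a stated rule for those.

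The cost of the recommended change is one phrase removed in two places and one sentence added. No new data are needed. The SE of the contrasts does not change in the balanced case and changes by about 1% at distance 4 in the unbalanced mix.

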7. SAP REPORTING GUIDELINE

This SAP has been reported according to the items recommended by the DEBATE guideline for statistical analysis plans for observational studies [8] adapted from Gamble et al. [9].

Table A. Recommended content of statistical analysis plans for observational studies

Section/Item	Index Description	Location in this SAP
Section 1: Administrative Information		
Title and trial registration	1a Descriptive title that matches the protocol, with SAP either as a forerunner or subtitle, and study acronym	Front page
	1b Study registration number	Front page
SAP version	2 SAP version number with dates	Front page
Protocol version	3 Reference to version of protocol being used	Front page
SAP revisions	4a SAP revision history	Front page
	4b Justification for each SAP revision	Front page
	4c Timing of SAP revisions in relation to planned repetitive analyses	Front page
Roles and responsibility	5 Names, affiliations, and roles of SAP contributors	Front page
Signatures of:	6a Person writing the SAP	Front page
	6b Senior statistician responsible	Front page
	6c Chief investigator/clinical lead	Front page
Section 2: Introduction		
Background and rationale	7 Synopsis of study background and rationale including a brief description of research question and brief justification for undertaking the study	1. Study overview
Objectives	8 Description of specific objectives and hypotheses, including secondary objectives	1. Study overview
Section 3: Study Methods		
Study design	9 Brief description of study design including type of study (e.g. case-control, cross-sectional or cohort study)	1. Study overview
Power considerations	10 In case of an unspecified sample size, provide power calculations for (at least) the primary analysis or present a detectable difference with a specified power	1. Study overview
Framework	11 Superiority, equivalence, or noninferiority hypothesis testing framework, including which comparisons will be presented on this basis	1. Study overview
Statistical interim analyses and stopping guidance	12a Information on repetitive analyses specifying what repetitive analyses will be carried out and listing of time points	1. Study overview
	12b Any planned adjustment of the significance level due to repetitive analyses	1. Study overview
	12c Details of guidelines for stopping the study early	-
Timing of final analysis	13 Timing of final analysis, e.g., all outcomes analysed collectively or timing stratified by planned length of follow-up	-
Timing of outcome assessments	14 Time points at which the outcomes are measured including visit "windows"	2. Tabular presentation of timing of outcome measurements
Section 4: Statistical Principles		
Confidence intervals and P values	15 Level of statistical significance	1. Study overview
	16 Description and rationale for any adjustment for multiplicity and, if so, detailing how the type 1 error is to be controlled	1. Study overview
	17 Confidence intervals to be reported	1. Study overview
Adherence and protocol deviations	18a Definition of protocol deviations for the study	4. Protocol deviations with bearing on this statistical analysis plan
	18b Description of which protocol deviations will be summarized	4. Protocol deviations with bearing on this statistical analysis plan
Analysis populations	19 Definition of analysis populations, eg, intention to treat, per protocol, complete case, safety	5. Outline (for each table and figure)

Section 5: Study Population			
Screening data	20	Reporting of screening data (if collected) to describe representativeness of trial sample	-
Eligibility	21	Summary of eligibility criteria	1. Study overview
Recruitment	22	Information to be included in the STROBE flow diagram	5. Outline (Figure 1)
Withdrawal/follow-up	23a	Level of withdrawal, e.g., dropouts after inclusion or refusal to be contacted for additional information	5. Outline (Figure 1)
	23b	Timing of withdrawal/lost to follow-up data	5. Outline (Figure 1)
	23c	Reasons and details of how withdrawal/lost to follow-up data will be presented	5. Outline (Figure 1)
Baseline patient characteristics	24a	List of baseline characteristics to be summarized	5. Outline (Table 1)
	24b	Details of how baseline characteristics will be descriptively summarized	5. Outline (Table 1)
Potential confounding covariates	25	A description of potential confounding covariates and how these will be dealt with	-
Section 6: Analysis			
Outcome definitions	List and describe each primary and secondary outcome including details of:		
	26a	Specification of outcomes and timings. If applicable include the order of importance of primary or key secondary endpoints (e.g., order in which they will be tested)	5. Outline (mainly Table 2)
	26b	Specific measurement and units (e.g., glucose control, HbA1c [mmol/mol or %])	5. Outline (Table 2)
	26c	Any calculation or transformation used to derive the outcome (e.g., change from baseline, QoL score, time to event, logarithm, etc)	5. Outline, and 3. Outcomes and data
Analysis methods	27a	What analysis method will be used and how the treatment effects will be presented	5. Outline
	27b	Any adjustment for covariates	5. Outline
	27c	Methods used for assumptions to be checked for statistical methods	5. Outline
	27d	Details of alternative methods to be used if distributional assumptions do not hold, eg, normality, proportional hazards, etc	5. Outline
	27e	Any planned sensitivity analyses for each outcome where applicable	5. Outline
	27f	Any planned subgroup analyses for each outcome including how subgroups are defined	5. Outline
Missing data	28	Reporting and assumptions/statistical methods to handle missing data (e.g., multiple imputation)	5. Outline
Additional analyses	29	Details of any additional statistical analyses required, eg, complier-average causal effect analysis	5. Outline
Harms	30	Only applies when intervention effects are studied. Sufficient detail on summarizing safety data, e.g. information on severity, expectedness, and associations; details of how adverse events are scored; how adverse event data will be analysed and the follow-up time.	-
Statistical software	31	Details of statistical packages to be used to carry out analyses	1. Study overview
References	32a	References to be provided for nonstandard statistical methods	6. References
	32b	Reference to Data Management Plan	-
	32c	Reference to the Study Master File and Statistical Master File	-
	32d	Reference to other standard operating procedures or documents to be adhered to	-

Abbreviations: STROBE, STrengthening the Reporting of OBservational studies in Epidemiology; HbA1c, hemoglobin A1c; QoL, quality of life; SAP, statistical analysis plan.
